Scientific rationale for the observation period: Studies in trauma patients have suggested the organ dysfunction that develops soon after trauma (i.e., during the first 48 -72 h) rapidly resolves in a high proportion of patients and may reflect the reversible derangement of organ function induced by the inciting event or incomplete resuscitation. Thus, it has been proposed that later assessment of organ function (i.e., 3 days after injury) will yield a more accurate definition of multiple organ failure in trauma patients, which is needed to evaluate the relationship between trauma-induced organ dysfunction and prognosis^{71,72}. In the acute phase, particularly the first 72 hours after severe burn injury, organ dysfunction frequently occurs, causing AKI (e.g., oliguria), cardiovascular dysfunction (e.g., hypotension), and coagulopathy (e.g., thrombocytopenia)⁷³. In some cases, the organ dysfunction is transient and the patient may recover during the late-acute or sub-acute phase. In such cases, the recovery from organ dysfunction is associated with relatively good prognosis. In contrast, if the organ dysfunction continues beyond the acute phase or if it occurs or recurs at a later time, the clinical outcome is typically worse. Therefore, we will evaluate the effects of

CoQ10 supplementation on the aforementioned multi-organ dysfunction that patients encounter beginning 72 hours post-burn injury and thereafter.

Secondary endpoints: Secondary endpoints will be the following outcome events observed from 72 hours after burn injury through 12 weeks or until death or discharge (whichever occurs first) and the biochemical measurements in plasma and urine.

1. The six individual binary outcome MODS events and their times of occurrences, (i.e., the constituents of the primary composite score)
2. Weighted composite score of the six constituents
3. Maximum total SOFA score
4. Maximum SOFA score for each organ
5. AUC of total SOFA score (score x days)
6. AUC of SOFA score for each organ (score x days)
7. Delirium (CAM-ICU) (number of days)
8. Length of hospital stay (number of days)
9. Sepsis (Sepsis-3) (number of incidence)
10. Septic Shock (Sepsis-3) (number of incidence)
11. Plasma mitochondrial DNA (4 blood collections)
12. 3-Methylhistidine (3-MH) and creatinine in urine (a biomarker of muscle wasting)

Scientific rationale for the clinical secondary endpoints: To comprehensively evaluate the effects of CoQ10 supplementation on dysfunction of organs and systems, we will examine total and individual scores of multiple organs/systems. Severity of multiple organ dysfunction is associated with the morbidity and mortality of burn victims. We will, therefore, evaluate weighted composite score of the six events that constitute the primary endpoint, where stages 1, 2 and 3 of AKI, and mild, moderate and severe ARDS are counted as score 1, 2 and 3, respectively. Regarding cardiovascular dysfunction, coagulopathy and liver dysfunction, we will use the SOFA scores (**Table 5**) for the weighted composite score. Moreover, over and above the maximum severity of organ dysfunction, its duration also affects the clinical trajectory of severely burned patients. Therefore, to take both severity and duration of organ dysfunction into account, we will analyze the area under the curve (AUC) for the SOFA score as previously described⁷⁴.

Our preclinical and pilot clinical studies suggest that CoQ10 supplementation may prevent the development and/or exacerbation of mitochondrial dysfunction/disintegrity and multi-organ dysfunction in burn victims. However, it is possible that CoQ10 supplementation may exert beneficial effects in the recovery phase as well as acute and subacute phases. We will, therefore, investigate the time-dependent effects of CoQ10 supplementation longitudinally.

Delirium, a common complication and significant clinical issue in burn patients, is associated with long-term outcome⁷⁵. [name] preliminary data showed in mice that mitochondrial dysfunction in the central nervous system plays a critical role in surgery/anesthesia-induced delirium⁷⁶. However, the effect of CoQ10 on delirium has not yet been studied in any disease. CAM-ICU will be used to assess delirium⁷⁷.

Sepsis and septic shock are major causes of mortality in burn patients. [name] preliminary study showed in mice that CoQ10 supplementation improved bacterial clearance and survival of septic mice and prevented inflammation organ inflammation (e.g., heart, liver, kidney). For the diagnosis of sepsis and septic shock, we will use the Third

International Consensus Definitions for Sepsis and Septic Shock (Sepsis-3) that was issued in 2016^{78,79}.

Scientific rationale for the biochemical secondary endpoints: To evaluate the effect of CoQ10 supplementation on systemic mitochondrial disintegrity, we will measure mtDNA abundance in the circulation. Mitochondrial disintegrity and apoptotic cell death have been implicated in the rise of circulating mtDNA. Moreover, circulating mtDNA functions as a damage-associated molecular pattern (DAMP), which induces and/or exacerbates systemic inflammatory response in major trauma^{29, 33}. In our pilot study, plasma mtDNA levels were significantly higher in burn patients compared with healthy controls. These results are consistent with previous studies in non- burn trauma patients. In our preclinical study in mice, burn caused an increase of mtDNA levels in plasma, which was mitigated by CoQ10 administration. Similarly, there was a trend toward decreased circulating mtDNA levels in the CoQ10 group compared with the placebo group ($P<0.10$), although statistical significance was not achieved possibly due to the small sample size ($n=15$ per group).

Muscle wasting is a major metabolic complication of burn injury and worsens the clinical outcome of burn patients. Muscle wasting interferes with the ability to wean off mechanical ventilation, recovery, and rehabilitation after burn injury. Moreover, muscle wasting is an essential component of burn cachexia and hypermetabolism, both of which are major contributors to worse prognosis after severe burn injury. Increased proteolysis is a major component of burn-induced muscle wasting. After burn injury, both breakdown and synthesis of proteins increase in skeletal muscle; however, the increase in protein breakdown exceeds that of protein synthesis, leading to muscle atrophy^{80,81}. To evaluate muscle wasting, therefore, we will measure 3-methylhistidine in 24-h urine samples, an indicator of protein breakdown in muscle, and normalize it to creatinine concentrations. Because 3-methylhistidine is present only in actin and myosin and is not reutilized for protein synthesis after it is released during proteolysis⁸², increased 3-methylhistidine-to-creatinine ratio in urine indicates accelerated myofibrillar protein breakdown⁸³. Burn injury increases 3- methylhistidine-to-creatinine ratio in human and rat urine^{52,53}.

Data Analysis: For between-arm comparisons of single valued (either measured at once or as an aggregated variable such as AUC over a period) outcomes, we will apply chi-square test if the outcome is binary, and *t*-test or Mann-Whitney *U*-test to continuous outcomes based on the best fit of Shapiro-Wilk's test. The between-arm difference in the distributions of times to the first event and multiple events (of the six constituents) will be examined by using single event time Cox's model and the times to correlated multiple events using Cox's model allowing multivariate frailty, respectively. The incidence rates of each individual event, with- and without differentiating its severity, as a binary outcome will be compared between the two arms by means of longitudinal logistic modeling with generalized estimating equation (GEE)⁸⁴ to allow more than one events per patient. For the repeated measures analysis of the longitudinal plasma mitochondrial DNA and urine 3- methylhistidine (3-MH), we will examine if the mean levels over time are different between the two arms by using longitudinal general linear mixed effects model⁸⁵ which will provide the within group time dependency patterns as a linear effect or more complex form of non-linear patterns which would be able to characterize the time dependent treatment effects over time along with testing for time \times group interaction(s) of those model parameter(s). Total and organ-specific SOFA scores over time will also be examined by this mixed effects models of which the

particular interest is to test if the improvement in the longitudinal mean SOFA scores is greater during certain time window. All analyses will also be extended to adjust for the influencing effects of any baseline demographic and/or clinical indications. Missing data may be unavoidable. Because the informed consent from many study enrollees will be obtained through the family members (i.e., surrogates), a small portion (up to 2% attrition rate) of the enrolled patients may voluntarily withdraw from the study. Before final analysis, we will check the missing data pattern of the outcomes first. If there are systematic differences in missing data patterns between the study groups and/or patient characteristics (e.g., burn type), we will take into account such problems in the analysis. The longitudinal mixed effects modeling will provide unbiased and consistent estimates of the effects provided that the missing data mechanism is ‘missing at random’ (MAR). If necessary, multiple-imputation will be applied to all endpoints analyses. All statistical tests will be two-sided and will adopt a 5% significance level.

Sample size calculation: The sample size of 290 study patients for this study is determined to achieve an adequate statistical power at a 5% Type-1 error rate for the primary endpoint analysis by the following statistical calculations. We first estimated the expected means and variances of the composite scores (assuming the six individual events are independent) for the Control and CoQ10 treatment arms under the assumption depicted in **Table 6** via 1000 repeated simulated data sets ($n = 5000$ each), instead of calculating them algebraically.

Each simulation run calculated the means and variances of the two arms, and the resulting average means (and variances) over 1000 simulations were 2.43 (1.04) in the placebo arm and 1.94 (1.05) in CoQ10 arm respectively. Based on the assumption about the event incidence rates and the estimated means and variances of the composite scores from the simulated data sets, the calculated required sample size per treatment arm (using PASS¹¹⁰) to detect such a difference (i.e., 20% reduction in the overall events) with 80% power at a 5% Type-1 error rate using 2-sided independent samples t-test was 142 per arm.

We have estimated the incidence rates of dysfunction of each organ or system and mortality under the null hypothesis (H_0), which are listed below in **Table 6** (Control Arm), based on previous studies^{6,46,48,59,60,64,74,86-95} and [name] pilot study.

Table 6. Elements of the composite endpoint and their assumed incidence rates	Control Incidence Rate	CoQ10 Incidence Rate
Acute Kidney Injury (KDIGO) (Stage 1 -3)	40%	32%
ARDS (Berlin Definition) (Mild – Severe)	40%	32%
Cardiovascular Dysfunction (Score 1 - 4)	70%	56%
Coagulopathy (Score 1 - 4)	70%	56%
Liver dysfunction (Score 1 - 4)	10%	8%
Death (All Causes)	8%	6.4%

Quarterly Enrollment Target: 290 burn patients will be enrolled at the 15 sites and each site is anticipated to enroll 19 patients during the study period. The quarterly enrollment targets are shown below in **Table 7**.

Table 7	Year 1				Year 2				Year 3				Year 4			
	Q1	Q2	Q3	Q4												

Quarterly	-	-	24	24	25	24	24	25	24	24	25	24	24	25	-	-
Cumulative	-	-	24	48	73	97	121	146	170	194	219	241	265	290	290	290

DATA MANAGEMENT AND DATE SAFETY MONITORING PLAN

Data management: Data will be housed in a secure database at the University of California Davis Data Coordinating Center (UCD-DCC). The UCD-DCC will utilize the RedCap data management tool to manage this clinical study. Records containing PHI will be managed according to the requirements of the HIPAA Privacy Rule. All subject case study forms and records will be de-identified and assigned a unique study number to protect patient privacy and maintain confidentiality. PHI will be maintained at the participating sites for the purpose of data verification. Any hard copy source documents will be stored in a locked file at each site for a minimum of three years after study closure and completion of analysis. If any information from this study is presented at scientific meetings or published, subject names and PHI will not be used.

Data safety monitoring plan and interim analysis: We will follow the guidelines of the DoD to form the Data Safety Monitoring Board (DSMB). The DSMB will monitor the overall status of the trial: number of patients enrolled overall and per each center, adherence to protocol overall and per center and results of the interim analysis.

Risk management and emergency response: We do not anticipate any severe adverse event (SAE) related to the supplement or placebo. No adverse events (AEs) occurred in [name] pilot study of CoQ10 that enrolled 30 burn patients. We will, however, establish risk management and emergency response plans. Site PIs and site Co-investigators will monitor the safety environment of the participants. If an adverse event (AE) or unanticipated problem occurs during the study period, it will be reported to the overall PI, the site PI, the overall study IRB, and the UCD-DCC. In that case the overall PI will report the AE to other site PIs. The site PI and/or overall PI will submit an expedited SAE report to the American Burn Association and the USAMRMC within 24 hours of the event being reported to the PI. The expedited report will be followed by a detailed, written SAE report. The DSMB will convene and decide necessary responses to unpredictable risks or changes in the protocols such as dose reduction and inclusion/exclusion criteria.

RISKS OF STUDY PARTICIPATION

Possible complications of non-surgical procedures: The blood samples will be withdrawn from an existing central IV line or venipuncture if a central IV line is not available. No new indwelling catheters will be placed in order to obtain blood samples. Blood draw from central venous lines may be associated to a small risk of infection; however the procedure will be only performed by authorized and experienced healthcare personnel. The risk of venipuncture is minimal. Hematoma formation and phlebitis are possible complications; however the occurrence is very rare with rapid resolution and venipuncture will be performed only when the patient needs other labs drawn in her/his clinical care.

Supplementation side effects and toxicities: Risks and discomfort associated with this

study will be small. CoQ10 is a nutrient and not a drug. [name] obtained an IND exemption from the FDA for his pilot study of CoQ10 supplementation (1,800 mg/day) in burn patients. The safety of CoQ10 and placebo supplementation in both tablet and liquid formulas has been shown in previous clinical studies in healthy subjects and patients with other disease conditions. High doses of CoQ10 (e.g., 2400 - 3,600 mg/day) have been used in clinical studies in the United States and the long-term safety of high-dose CoQ10 (3,000 mg/day or 3,600 mg/day) has been shown in patients with Huntington's disease, amyotrophic lateral sclerosis (ALS) and Parkinson's disease, and in healthy subjects. To date, no serious adverse side effect of CoQ10 has been reported regardless of the dosage. Side effects are typically mild and brief, stopping without any treatment needed. Reactions are rare but may include nausea, vomiting, stomach upset, heartburn, diarrhea, loss of appetite, skin itching, rash, insomnia, headache, dizziness, increased light sensitivity of the eyes, fatigue, or flu-like symptoms. There may be other risks that are currently unknown about supplementation of CoQ10 or placebo.

Psychosocial (non-medical) risks: Other potential major risks involve privacy concerns. As such, all data will be coded and only available to the immediate research team and the UCD-DCC. Data will be stored in the HIPPA- compliant REDCap ([Research Data Capture](#)) system. Whole blood samples will be labeled according to an established code to be able to identify patients when/if needed. All samples will be stored in a secure -80°C freezer at UTMB. Subject identifying information and the informed consent will be maintained in a locked cabinet in a locked room in the Clinical Research Department of each study site. Results obtained from individual subjects will be analyzed, reported, and discussed in reference to Subject ID only. All investigators and study staff are required to receive training in the ethical use of humans in research. We will not obtain any genetic information, such as DNA sequence, single-nucleotide polymorphism, haplotype and gene expression, although we will measure total amounts of mitochondrial DNA in plasma.

IND EXEMPTION

Given that CoQ10 is classified as a nutrient, [name] received an IND exemption for the original pilot trial. As we will be using the same preparation in the same route of administration and in the same dosage ranges, we do not have plans to repeat obtaining an IND exemption for the present study.

PROJECT MILESTONES

(1) Regulatory documents and research protocols (1-6 months): It will take at least 2- 3 months for regulatory review and approval of this clinical trial by the USAMRMC Human Research Protection Office (HRPO). In the meantime, the protocol will be reviewed and approved by the UT Southwestern (UTSW) Institutional Review Board (IRB). As an institution, UTSW participates in SmartIRB, a platform designed to facilitate multicenter clinical research among participating institutions through single IRB reliance. We anticipate that the overall PI will have the protocol approved by the UTSW IRB prior to the funding start date and will have secured IRB reliance from the other 14 participating centers. A Data Safety Monitoring Board (DSMB) will be formed.

(2) Inception of patient enrollment: After the IRB protocols are approved and data and sample collection methods are confirmed by site visits of the overall PI and the data management staff of the UCD-DCC within the first 6 months of Year 1, we will start enrollment of eligible patients by month 6. Human subjects protection, compliance, quality of data collection, and pace of enrollment will be monitored by the DSMB, the UCD-DCC, and the overall and site PIs.

(3) Data analysis and reports: In the latter half of Year 4, we will perform all the statistical analyses of clinical data and biomarkers and write reports and a manuscript.

REFERENCES

1. Klein MB, Goverman J, Hayden DL, Fagan SP, McDonald-Smith GP, Alexander AK, Gamelli RL, Gibran NS, Finnerty CC, Jeschke MG, Arnoldo B, Wispelwey B, Mindrinos MN, Xiao W, Honari SE, Mason PH, Schoenfeld DA, Herndon DN, Tompkins RG: Benchmarking outcomes in the critically injured burn patient. *Ann Surg* 259:833-841
2. Arulkumaran N, Deutschman CS, Pinsky MR, Zuckerbraun B, Schumacker PT, Gomez H, Gomez A, Murray P, Kellum JA: Mitochondrial Function in Sepsis. *Shock* 45:271-281
3. Duran-Bedolla J, Montes de Oca-Sandoval MA, Saldana-Navor V, Villalobos-Silva JA, Rodriguez MC, Rivas-Arancibia S: Sepsis, mitochondrial failure and multiple organ dysfunction. *Clin Invest Med* 37:E58-69

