Brief study overview: We will conduct a two-arm, prospective, double-blind, randomized, placebo-controlled clinical trial to evaluate the efficacy and safety of reduced form CoQ10 (ubiquinol) supplementation in severely burned adult patients (total n=290) at 15 mature burn centers across North America. Stratified block randomization will take place by site and Revised Baux score. The formula for the Revised Baux score is: Age + Percent Burn (%TBSA) + 17 x (Inhalation Injury, 1 = yes, 0 = no). This formula has been widely adopted for mortality prediction in burn patients^{45,46}. In previous studies, a trend has been shown for a sharp increase in mortality when the Revised Baux score exceeds approximately 110^{45,47,48}. Therefore, patients enrolled in this study will be stratified for randomization into two groups based on the Revised Baux score: (1) less than 110; and (2) equal to or greater than 110. The intervention will consist of a loading dose of reduced form CoQ10 of 1,800 mg/day tid for 4 weeks to be followed by a maintenance dose of 600 mg/day once daily from weeks 5 to 12. The intervention or allocation-controlled placebo will be administered by 72 hours after injury and will continue until 12 weeks after injury or until death or discharge, whichever comes first. Oral tablets (600 mg/tablet) will be administered to CoQ10 subjects who can swallow while a liquid form (100 mg/mL) will be administered to CoQ10 subjects requiring an enteral tube for nutrition. There will be no post-discharge study procedures.

Study investigators, personnel, and centers:

[name] MD, MSCS; UT Southwestern Medical Center/Parkland Memorial Hospital
[name]; Wake Forest University School of Medicine
[name]; University of Texas Medical Branch- Galveston
[name]; The Ohio State University Wexner Medical Center
[name]; University of Alabama-Birmingham Medical Center
[name]; University of Kansas Medical Center
[name]; University of Michigan
[name]; Case Western Reserve University School of Medicine
[name]; Massachusetts General Hospital
[name]; Loyola University Medical Center
[name]; Temple University
[name]; Columbia St. Mary's-Wisconsin
[name]; University of California- Davis
[name]; University of South Florida
[name], MD; University of South Florida
[name]; Hennepin County Medical center

[name], CRA; American Burn Association

[name], MSN; UC Davis, American Burn Association

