In compliance with the guidelines, the following categories of surrogates (listed in preferred order) may provide consent in writing on behalf of potential subjects incapable of providing informed consent: i) court appointed guardian with specific authority to consent to participation in research or authority to make health care decisions for a class of diagnostic and therapeutic decisions inclusive of the proposed research; ii) health care proxy/person with durable power of attorney with specific authority for making health care decisions inclusive of the proposed research; or iii) spouse, adult child, or other close family member who knows the subject well and has been involved in their care. Assent of subjects will be a requirement for participation in the research unless the subject is incapable of giving assent due to his/her medical condition. A licensed physician colleague or a well-trained study investigator will obtain informed consent. Participants will be given as much time as necessary to consider participation or to discuss the study with anyone before making a decision. Routine care will be provided to the patient regardless of enrollment to the study. This fact will be explained to the patients and/or legal guardian.

Randomization procedure: Permuted-block randomization stratified by study site and Revised Baux score will be performed. This study procedure will utilize the RS2 system that was developed by the ABA's Data Coordinating Center (DCC) based out of UC-Davis and which has been used in previous burn trials successfully.

Study population:

Table 2.	
----------	--

Inclusion Criteria	Rationale
Age 18 years and older	Military age subjects. There are no limitations on gender, race, or ethnicity.
Burn patients with 20% or greater of total body surface area (TBSA) burn and equal to or less than 70% TBSA burn	Burns greater than 20% are considered to be severe and potentially life threatening. Burns larger than 70% carry an excessive mortality and confound the primary endpoint of MODS
Capable of receiving routine oral, enteral nutrition, or a combination of routine oral and enteral nutrition	CoQ10 is not available in injectable form for humans. The enrolled patients will receive tablets (softgels) or liquid form of CoQ10 or placebo.
Enrolled within 72 hours after burn injury	This timepoint is early enough that a preventative effect of CoQ10 replacement can manifest

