Patient or legally authorized representative (LAR) who is capable of giving full informed consent	Principle of autonomy
Anticipated hospital stay: 2 weeks or more	This duration is the common timeframe for MODS development should it occur.
Exclusion Criteria	Rationale
Patients with liver disease (bilirubin greater than 3 or diagnosis of liver cirrhosis) at the time of admission, hyperthyroidism that currently requires treatment, diagnosis of chronic heart failure, chronic renal failure requiring hemodialysis, malignancy currently undergoing treatment, or history of cancer or hematological malignancy treatment within 5 years	The primary endpoint of MODS scoring is intended for acute organ dysfunction. Subjects with chronic, pre-existing organ dysfunction are confounders
History of HIV or AIDS	MODS is driven by the immune system so pre-existing immune dysfunction is a confounder
Presence of concurrent injuries apart from burn injury that may produce long-term disabilities (e.g., spinal cord injury, anoxic brain injury)	Nonthermal injury is a MODS risk by itself and therefore methodologically problematic

Participation in another research study that may confound the results of this study in the opinion of the site principal investigator	Concurrent enrollments in prospective studies with non-competing endpoints are common events in academic burn centers
Pregnant women	Vulnerable population
Prisoners	Vulnerable population

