3-Methylhistidine concentrations will be quantified by negative chemical ionization gas chromatography mass spectrometry as described in our previous studies^{52,53}. Urinary creatinine concentrations will be measured by a commercial kit. The average of three measurements on the three consecutive days at each time point will be used for statistical analysis to minimize possible day-to-day variations.

STATISTICAL ENDPOINTS AND APPROACH TO DATA ANALYSIS

This two-arm balanced double blind parallel Randomized Clinical Trial (RCT) study will be performed using an intention to treat (ITT) analysis population that includes all randomized patients.

Primary endpoint: The primary endpoint will be the count of the following events. This count will be used to create a composite score ranging from 0 to 6 by assigning 1 to each event regardless of stage, scores and severity that individual subjects encounter from 72 hours after burn injury through 12 weeks or until death or discharge, whichever occurs first:

1. Acute Kidney Injury (AKI) (KDIGO Stages 1 – 3)
2. ARDS (The Berlin ARDS Definition: Mild, Moderate, Severe)
3. Cardiovascular Dysfunction (SOFA Scores 1 – 4)
4. Coagulopathy (SOFA Scores 1 – 4)
5. Liver dysfunction (SOFA Scores 1 – 4)
6. Death (all causes)

We will calculate mean values of the composite sum scores among the study patients in the CoQ10 and placebo arms, and then test their difference by using an independent samples *t*-test if the observed data are evident to follow a normal distribution by Shapiro-Wilk's test. Otherwise, Mann-Whitney U test will be applied and the group specific medians and quartiles will be used as the summary statistics.

AKI: AKI represents the acute loss of kidney function and is associated with a profound and severe increase in morbidity and mortality in burn patients⁵⁴. Early AKI, which occurs less than 3 days post-burn, is usually related to inadequate fluid replacement during the initial resuscitation. AKI can occur later in the hospitalization and late AKI is multifactorial in origin and often associated with sepsis development⁵⁵. For the purposes of this study, we will follow the definitions and classification guidelines set forth in "AKI of Kidney Disease: Improving Global Outcomes (KDIGO)"^{56,57} (**Table 3**). Published in 2012, this guideline has been used in critically ill patients and in combat-injured populations⁵⁸.

Stage	Table 3. AKI (KDIGO)

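### All-cause death is counted only from 72 hours after burn, although patients are randomised and dosed before then, so a death before 72 hours enters no planned efficacy analysis

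*Combined protocol and SAP*

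**What the plan says.** All references are to the combined protocol and SAP.

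- **Entry and dosing.** Table 2 requires patients to be "Enrolled within 72 hours after burn injury". The Brief study overview adds: "The intervention or allocation-controlled placebo will be administered by 72 hours after injury". Time on study before 72 hours is therefore part of the design.
- **Population.** The opening of the statistical section specifies an "intention to treat (ITT) analysis population that includes all randomized patients".
- **Primary endpoint.** The 0 to 6 score is formed "by assigning 1 to each event regardless of stage, scores and severity that individual subjects encounter from 72 hours after burn injury". The window ends at 12 weeks, death or discharge. All-cause death is the sixth event and has no start time of its own.
- **Secondary endpoints.** "Secondary endpoints will be the following outcome events observed from 72 hours after burn injury through 12 weeks or until death or discharge". Death appears there only as one of the six constituents. The chi-square, Cox and GEE comparisons of those constituents under Data Analysis therefore use the same start.
- **Reason for the 72-hour start.** The rationale for the observation period argues that early dysfunction may resolve: "In some cases, the organ dysfunction is transient and the patient may recover during the late-acute or sub-acute phase".

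No section says how to score a randomised patient who dies before 72 hours.

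**The concern.** The 72-hour start suits the five organ events, which can be reversed by resuscitation. Death cannot be reversed, so the argument for the delay does not carry over to it. Applying one window to all six events leaves a post-randomisation interval in which the most serious outcome is not counted.

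Taken literally, such a patient stays in the intention-to-treat analysis with a score of 0. An early death would then rank among the best results, and an excess of early deaths in one arm would favour that arm. The mortality comparison would also no longer cover all deaths among randomised patients.

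**Working it through.** The plan gives no figure for deaths before 72 hours, so there is none to reproduce. The steps below size the problem from the plan's own inputs.

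**Inputs.** There are 290 patients in two balanced arms, so 145 per arm. Table 6 gives death rates of 8% (placebo) and 6.4% (CoQ10), and placebo organ-event rates of 40%, 40%, 70%, 70% and 10%. Sample size calculation gives means of 2.43 and 1.94 (difference 0.49) and variances of 1.04 and 1.05.

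**1. How unusual a score of 0 is.** Under Table 6 with independent events, as the plan assumes:
- Placebo: 0.6 × 0.6 × 0.3 × 0.3 × 0.9 × 0.92 = 2.7%.
- CoQ10: 0.68 × 0.68 × 0.44 × 0.44 × 0.92 × 0.936 = 7.7%.

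**2. How many deaths.** Expected deaths are 145 × 0.08 = 11.6 and 145 × 0.064 = 9.28, total 20.88. Let f be the share of them falling before 72 hours. The documents do not give f, so it is assumed. With Poisson counts, P(at least one) = 1 − exp(−20.88 f).

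| f (assumed) | Expected early deaths, placebo / CoQ10 | P(at least one in trial) | P(arms differ by 3 or more) |
|---|---|---|---|
| 1% | 0.12 / 0.09 | 19% | 0.03% |
| 2% | 0.23 / 0.19 | 34% | 0.2% |
| 5% | 0.58 / 0.46 | 65% | 2% |
| 10% | 1.16 / 0.93 | 88% | 8% |
| 20% | 2.32 / 1.86 | 98% | 22% |

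**3. Shift in the arm mean.** The five placebo organ rates sum to 2.30. One early death scored 0, instead of an average survivor's organ count, lowers the arm mean by 2.30/145 = 0.016, which is 3.2% of 0.49. The standard error of the difference is √((1.04 + 1.05)/145) = 0.12. Counting the death as 1 restores 1/145 = 0.007, or 1.4% of 0.49.

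**4. Primary test.** In simulation the Shapiro-Wilk check rejected normality in all 1,000 placebo arms of 145, so the Mann-Whitney test would apply. With no treatment effect, placebo rates in both arms and independent events:
- *Unconditional.* Early deaths occur at the same rate in both arms and score 0. Across simulations at f = 0%, 10% and 20%, the two-sided error stayed between 4.8% and 5.2%.
- *Conditional on an excess in one arm.* With 1, 2 or 3 extra zero-scored deaths in one arm, the chance of falsely favouring that arm rises from 2.5% to about 3.1%, 3.7–4.0% or 4.6–4.8%.

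**5. Mortality risk ratio.** Planned: 9.28/11.6 = 0.80. One death omitted from CoQ10: 8.28/11.6 = 0.71. One omitted from placebo: 9.28/10.6 = 0.88. The log standard error is √(1/9.28 − 1/145 + 1/11.6 − 1/145) = 0.42, so the approximate 95% interval is exp(ln 0.80 ± 1.96 × 0.42), or 0.35 to 1.84. Power for 8.0% against 6.4% at 145 per arm is about 8%.

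**The case against.** The strongest reply is that this is a silence in the plan rather than a rule that rewards early death. The window closes at death, so a patient who dies before it opens has an empty window, and the score is arguably undefined. Data Analysis provides for examining missing-data patterns and for multiple imputation if necessary. That reading is available, and a reader who infers that the plan firmly assigns such a patient the best value goes too far. It does not rescue the wording, however, because an observed death would then be imputed as though the outcome were unknown.

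The second reply is rarity, and it stands. Exposure before 72 hours is short. Entry requires "Anticipated hospital stay: 2 weeks or more", and the burn-size cap is explained by "Burns larger than 70% carry an excessive mortality and confound the primary endpoint of MODS". An expected stay is a forecast, though, and does not rule out an early death. The values of f are assumptions. If Table 6 already refers to deaths inside the window, early deaths would be additional to those rates rather than a share of them.

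Third, a reader might infer an inflated type I error from the conditional figures. They fix an excess in one named arm. Without that condition the error stays near 5% if treatment does not affect early death, and the documents offer no evidence of such an early effect.

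Fourth, the correction changes the primary result very little. With 10% of deaths assumed early, Mann-Whitney power moves from 96.8% to 97.0% (83.7% to 84.7% at a correlation of 0.3 between events). This stands, and it limits the priority.

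Finally, early deaths would be reported under Risk management and emergency response. That covers safety, but puts them in no planned between-arm efficacy comparison.

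**Conclusion.** The endpoint definition is wrong as written for one type of patient, and the priority is minor. A death between randomisation and 72 hours is either counted as 0 or left undefined, and in both cases enters no planned efficacy analysis. The plan's rationale for the delay does not cover death. This part rests on the wording alone.

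The size rests on an assumed share of early deaths, and it is small. Each one shifts an arm mean by about 3% of the planned difference, overall type I error is essentially unaffected, and one omitted death moves the mortality risk ratio by far less than its sampling uncertainty. Only a chance or real excess of early deaths in one arm would favour that arm. The simulations assume Table 6 rates and do not truncate organ events at later deaths. The documents do not support a claim that the primary conclusion is at risk.

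**What to change.** Amend the endpoint wording before unblinding:

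1. Count death from any cause, as one point, from randomisation to the end of the existing window, in the primary score and in every secondary analysis of death.
2. Keep the 72-hour start for the five organ events.
3. State that a death before 72 hours is an observed outcome and is not imputed.

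A sensitivity analysis giving early deaths the worst score of 6 is not recommended. A death at 71 hours would score 6 while a death at 73 hours with no organ event would score 1, and nothing in the plan supports that contrast.

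The cost is one amendment through the single IRB and the relying centres described under Project Milestones. The sample size and the primary test stay as planned. No new data collection should be needed, since early deaths would already be known through adverse event reporting.
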